Appendix A

1f	Active endocarditis	
Measured 180 days prior to and including day of drug initiation in any diagnosis position and inpatient or outpatient care setting:
 
Endocarditis: ICD-9 diagnosis: 421.xx , 424.9x ICD-10 diagnosis: I33.xx, I38.xx, I39.xx
	
Tan, Charlie et al. "Accuracy of administrative data for identification of patients with infective endocarditis." International journal of cardiology vol. 224 (2016): 162-164. doi:10.1016/j.ijcard.2016.09.030

2	Hemorrhage Risk-Related Criteria		
2a	Active internal bleeding	
Measured 180 days prior to and including day of drug initiation in any diagnosis position and inpatient or outpatient care setting: Refer to the 'Bleeding' sheet for detailed codes (includes GI bleeding, intracranial, intra-articular bleeding mentioned in exclusion 2b)
	
2b	
History of or condition associated with increased bleeding risk including, but not limited to:
 
 - Major surgical procedure or trauma within 30 days before the randomization visit - Clinically significant gastrointestinal bleeding within 6 months before the randomization visit - History of intracranial, intraocular, spinal, or atraumatic intra-articular bleeding - Chronic hemorrhagic disorder - Known intracranial neoplasm, arteriovenous malformation, or aneurysm 	
Measured 30 days prior to and including day of drug initiation in diagnosis position and inpatient or outpatient care setting:
 
1) Major surgery: Major surgery selected from procedure codes range 40.x- 84.x -OR-
 
2) Hemorrhagic disorder (Bleeding diathesis) 286.x Coagulation defects 287.x Purpura and other hemorrhagic conditions -OR-
 
3) Intracranial neoplasm, AV malformation, aneurysm Intracranial neoplasm ICD-9 diagnosis: 225.xx ICD-10 diagnosis: D33.xx AV malformation ICD-9 diagnosis: 747.81 ICD-10 diagnosis: Q28.2x Cerebral aneurysm: ICD-9 diagnosis: 437.3x ICD-10 diagnosis: I67.1
	
2c	Planned invasive procedure with potential for uncontrolled bleeding, including major surgery	N/A	
2d	Platelet count <90,000/ μ L at the screening visit	
Measured 30 days prior to and including day of drug initiation in any diagnosis position and inpatient or outpatient care setting:
 
Thrombocytopenia: ICD-9 diagnosis: 287.3x, 287.4x, 287.5x
	
2e	Sustained uncontrolled hypertension: systolic blood pressure \geq 180 mmHg or diastolic blood pressure \geq 100 mmHg	
Measured 180 days prior to and including day of drug initiation in any diagnosis position and Inpatient care or ED setting:
 
Malignant hypertension: ICD-9 diagnosis: 401.0x Hypertensive urgency/Hypertensive crisis: ICD-10 diagnosis: I16.x
	
3	Concomitant Conditions and Therapies		
3a	Severe, disabling stroke (modified Rankin score of 4 to 5, inclusive) within 3 months or any stroke within 14 days before the randomization visit	
1) Measured 90 days prior to and including day of drug initiation in position and care setting specified below:
 
Stroke(primary diagnosis position, inpatient care setting): ICD-9 diagnosis: 430.xx, 431.xx, 433.xx, 434.xx, 436.xx,
 
-PLUS-
 
Disabling stroke effects (any position, any care setting, with 7-83 days between the strokes) ICD-9 diagnosis: 438.xx Late effects of cerebrovascular disease ICD-10 diagnosis: I69.xx Sequela of cerebrovascular disease (hemiplegia etc); Z73.6x Limitation of activities due to disability
 
2) Measured 14 days prior to and including day of drug initiation in primary diagnosis position and inpatient care setting:
 
Stroke: ICD-9 diagnosis: 430.xx, 431.xx, 433.xx, 434.xx, 436.xx
	
Patorno, Elisabetta et al. "Cardiovascular outcomes associated with canagliflozin versus other non-gliflozin antidiabetic drugs: population based cohort study." BMJ 2018;360:k119 http://dx.doi.org/10.1136/bmj.k119
 
Patorno, Elisabetta et al. "Empagliflozin and the Risk of Heart Failure Hospitalization in Routine Clinical Care: A First Analysis from the Empagliflozin Comparative Effectiveness and Safety (EMPRISE) Study." Circulation. 2019 Apr 8. doi: 10.1161/CIRCULATIONAHA.118.039177

3b	Transient ischemic attack within 3 days before the randomization visit	
Measured 3 days prior to and including day of drug initiation in primary diagnosis position and inpatient care or ED setting:
 
TIA: ICD-9 diagnosis: 435.xx
	

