5.3 Flowchart of the study cohort assembly

For rivaroxaban vs. warfarin

	Optum		Truven		Medicare	
	Less Excluded Patients	Remaining Patients	Less Excluded Patients	Remaining Patients	Less Excluded Patients	Remaining Patients
All patients		75,894,642		200,203,908		6,886,908
Did not meet cohort entry criteria	-74,960,282	934,360	-199,073,812	1,130,096	-2,028,461	4,858,447
Excluded due to insufficient enrollment	-92,301	842,059	-95,091	1,035,005	-1,551,114	3,307,333

Excluded due to prior use of referent	-482,398	359,661	-622,538	412,467	-2,080,069	1,227,264
Excluded due to prior use of exposure	-205,565	154,096	-204,425	208,042	-660,796	566,468
Excluded because patient qualified in >1 exposure category	-7	154,089	-26	208,016	-81	566,387
Excluded based on Age	-624	153,465	0	208,016	-155	566,232
Excluded based on Gender	0	153,465	0	208,016	0	566,232
Excluded based on Inclusion #1 - Age >=18	-86	153,379	-264	207,752	-65	566,167
Excluded based on Inclusion #2 & 3 - Atrial fibrillation	-83,438	69,941	-129,172	78,580	-348,521	217,646
Excluded based on Inclusion #4	-13,297	56,644	-16,046	62,534	-36,136	181,510
Excluded based on Exclusion #1a - Mitral stenosis	-275	56,369	-154	62,380	-399	181,111
Excluded based on Exclusion #1b - Prosthetic heart valve	-1,238	55,131	-789	61,591	-3,016	178,095
Excluded based on Exclusion #1e - atrial myxoma or left ventricular thrombus	-158	54,973	-35	61,556	-234	177,861
Excluded based on Exclusion #1f - Active infective endocarditis	-279	54,694	-138	61,418	-401	177,460
Excluded based on Exclusion #2a - Active bleeding or bleeding history	-3,413	51,281	-2,716	58,702	-8,256	169,204
Excluded based on Exclusion #2b.1 - Major Surgery	-1,564	49,717	-1,561	57,141	-6,484	162,720
Excluded based on Exclusion #2b.2 - Bleeding diathesis	-1,235	48,482	-885	56,256	-3,832	158,888
Excluded based on Exclusion #2b.3 - Intracranial neoplasm, AV malformation, cerebral aneurysm	-259	48,223	-283	55,973	-422	158,466
Excluded based on Exclusion #2d - Thrombocytopenia	0	48,223	0	55,973	0	158,466
Excluded based on Exclusion #2e - Uncontrolled hypertension	-47	48,176	-105	55,868	-300	158,166
Excluded based on Exclusion #3a.1 - stroke plus disabling stroke effects	-257	47,919	-152	55,716	-847	157,319
Excluded based on Exclusion # 3a.2 - stroke	-103	47,816	-88	55,628	-642	156,677
Excluded based on Exclusion #3b - TIA	-17	47,799	-25	55,603	-123	156,554
Excluded based on Exclusion #3c - DVT & PE	-1,095	46,704	-853	54,750	-3,185	153,369

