3	Non-valvular Atrial fibrillation Subjects with newly diagnosed atrial fibrillation are eligible provided that: - there is evidence that the atrial fibrillation is non-valvular - cardioversion is not planned - there is ECG evidence on 2 occasions 24 hours apart demonstrating atrial fibrillation			
	For Inclusion Criteria 4 It is either A) History of ischemic stroke or TIA or arterial embolism -OR- B) 2 of the following 4 1) Heart failure 2) Hypertension 3) Age >=75 4) Diabetes			
4	History of prior ischemic stroke, TIA or non-CNS systemic embolism believed to be cardioembolic in origin	Measured any time prior to and including day of drug initiation in any diagnosis position and inpatient or outpatient care setting: Ischemic stroke: ICD-9 diagnosis: 433.x, 434. x, 436.xx TIA: ICD-9 diagnosis: 435.xx Systemic embolism: ICD-9 diagnosis: 444.xx	
Patorno, Elisabetta et al. "Cardiovascular outcomes associated with canagliflozin versus other non-gliflozin antidiabetic drugs: population based cohort study." BMJ 2018;360:k119 http://dx.doi.org/10.1136/bmj.k119
 
Patorno, Elisabetta et al. "Empagliflozin and the Risk of Heart Failure Hospitalization in Routine Clinical Care: A First Analysis from the Empagliflozin Comparative Effectiveness and Safety (EMPRISE) Study." Circulation. 2019 Apr 8. doi: 10.1161/CIRCULATIONAHA.118.039177
	
	OR 2 or more of the following risk factors	Measured anytime prior to and including day of drug initiation in any diagnosis position and inpatient or outpatient care setting:		
4a	– Heart failure and/or left ventricular ejection fraction ≤35%	Heart failure: ICD-9 diagnosis: 428.x, 398.91, 402.01, 402.11, 402.91, 404.01, 404.11, 404.91, 404.03, 404.13, 404.93	
Patorno, Elisabetta et al. "Cardiovascular outcomes associated with canagliflozin versus other non-gliflozin antidiabetic drugs: population based cohort study." BMJ 2018;360:k119 http://dx.doi.org/10.1136/bmj.k119
 
Patorno, Elisabetta et al. "Empagliflozin and the Risk of Heart Failure Hospitalization in Routine Clinical Care: A First Analysis from the Empagliflozin Comparative Effectiveness and Safety (EMPRISE) Study." Circulation. 2019 Apr 8. doi: 10.1161/CIRCULATIONAHA.118.039177
	

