1e	Known presence of atrial myxoma or left ventricular thrombus	
Measured 180 days prior to and including day of drug initiation in any diagnosis position and inpatient or outpatient care setting:
 
Atrial myxoma: ICD-9 diagnosis: 212.7 (Benign neoplasm of heart) ICD-10 diagnosis: D15.1 (Benign neoplasm of heart)
 
Left ventricular thrombus: ICD-10 diagnosis: I51.3 (Intracardiac thrombosis)
	Joshi, Kirti K et al. "Postoperative atrial fibrillation in patients undergoing non-cardiac non-thoracic surgery: A practical approach for the hospitalist." Hospital practice (1995) vol. 43,4 (2015): 235-44. doi:10.1080/21548331.2015.1096181

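### Exclusion 2b applies the trial's 30-day surgery window to bleeding disorders and intracranial lesions, for which the trial set no time limit

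*Combined protocol and SAP*

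**What the plan says.** Appendix A sets each trial criterion beside its claims implementation. In row 2b the trial column names five conditions and puts a time limit on two: "Major surgical procedure or trauma within 30 days before the randomization visit", and clinically significant GI bleeding (6 months). The other three have no limit: a history of intracranial, intraocular, spinal or atraumatic intra-articular bleeding; "Chronic hemorrhagic disorder"; and "Known intracranial neoplasm, arteriovenous malformation, or aneurysm".

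The implementation column opens with a single header, "Measured 30 days prior to and including day of drug initiation in diagnosis position and inpatient or outpatient care setting". Three items joined by OR follow:

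1. major surgery;
2. hemorrhagic disorder (286.x, 287.x);
3. intracranial neoplasm, AV malformation or cerebral aneurysm.

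No reason is given for using one window for all three.

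Two neighbouring rows matter. Exclusion 2a covers bleeding events over 180 days, with a code list that, by its own note, "includes GI bleeding, intracranial, intra-articular bleeding mentioned in exclusion 2b". Exclusion 2d covers thrombocytopenia (287.3x, 287.4x, 287.5x) over 30 days, standing in for a platelet count at the trial's screening visit.

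**The concern.** A clotting disorder, an unruptured aneurysm or a vascular malformation does not lapse because no claim carried its code in the last month. A short window suits an acute event such as surgery. For a standing condition it makes eligibility depend on when the code was last billed.

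The trial excluded these patients for bleeding risk. Hemorrhagic stroke is part of the primary outcome and major bleeding is the control outcome (Section 6.3.1). Section 5.2.2 says the criteria follow the trial as closely as possible. Appendix B has no row specific to intracranial neoplasm, malformation, aneurysm or coagulation defect, so balance on whatever remains cannot be checked directly.

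**Working it through.** **Step 1: compare 2b with the plan's own practice.**

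| Criterion (Appendix A) | Trial time limit | Window in claims |
|---|---|---|
| 1a mitral stenosis | none | 180 days |
| 1b prosthetic valve | none | 180 days |
| 1e known myxoma or LV thrombus | none | 180 days |
| 3k HIV | at screening | 180 days |
| 3m liver disease | none | 180 days |
| 2b item 1, surgery | 30 days | 30 days |
| 2b item 2, hemorrhagic disorder | none | 30 days |
| 2b item 3, intracranial lesions | none | 30 days |

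Row 1e, also a known-presence criterion, reads "Measured 180 days prior to and including day of drug initiation in any diagnosis position and inpatient or outpatient care setting". Inclusion 4 goes further: "Measured any time prior to and including day of drug initiation in any diagnosis position and inpatient or outpatient care setting". Where a row needs several windows the plan writes them out: 3a has 90 and 14 days, and 3d has 180, 10 and 5 days. Row 2b does not, so on its face the 30 days governs all three items.

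**Step 2: reproduce the flowchart (Section 5.3).** The row "Excluded based on Exclusion #2b.2 - Bleeding diathesis" and the next one give:

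- Optum: 49,717 − 1,235 = 48,482; 48,482 − 259 = 48,223.
- Truven: 57,141 − 885 = 56,256; 56,256 − 283 = 55,973.
- Medicare: 162,720 − 3,832 = 158,888; 158,888 − 422 = 158,466.

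All agree with the printed figures. Item 2 removed 2.48%, 1.55% and 2.35%; pooled 5,952/269,578 = 2.2%. Item 3 removed 0.53%, 0.50% and 0.27%; pooled 964/263,626 = 0.37%. These are patients caught. No count of patients with an older code is given.

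**Step 3: ask how much a 30-day window might miss.** The only internal evidence is indirect. Appendix B (unmatched, pooled) reports some utilization both for the last 30 days and for the baseline. With both arms added, the share of patients with a baseline record who also had one in the last 30 days is:

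- cardiologist visit: (68,742 + 46,689)/(106,124 + 58,289) = 70%;
- internal or family medicine visit: (86,911 + 45,400)/(127,845 + 63,665) = 69%;
- hospitalization: (30,123 + 20,297)/(49,023 + 30,191) = 64%;
- endocrinologist visit: (2,038 + 1,197)/(6,566 + 3,534) = 32%.

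If diagnosis coding behaved like these contacts (an assumption), 30 days would miss about 30% to 68% of patients with a code in the 180-day baseline. The loss against full history would be larger.

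**Step 4: put a rough scale on it, under the same assumption.** If a share c is caught, those missed number removed × (1 − c)/c.

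- Item 3: 964 × 0.298/0.702 ≈ 409, up to 964 × 0.680/0.320 ≈ 2,050.
- Items 2 and 3: 6,916 × 0.298/0.702 ≈ 2,900, up to 6,916 × 0.680/0.320 ≈ 14,700. That is 1.1% to 5.6% of the 262,662 remaining after 2b.3, before later exclusions.

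The second range includes the thrombocytopenia codes within 287.x, which the fix below leaves at 30 days, so it overstates what the fix would remove.

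**Step 5: check the overlap with 2d.** Item 2 takes all of 287.x, which contains 2d's 287.3x-287.5x. The flowchart shows 2d removing 0 patients in every database after 2b.2, as this overlap would produce. Widening all of 287.x to 180 days would therefore override 2d's own window.

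**The case against.** The strongest reply is that the damage is unmeasured and partly covered. Bleeding events are excluded over 180 days under 2a. After matching, HAS-BLED is 3.47 in both arms, intracranial or retroperitoneal hemorrhage is 129 versus 128 patients, and other cerebrovascular disease is 2,364 versus 2,302. Item 3 is small, and nothing shows that retained patients differ by arm. All of this stands, and it limits the point to fidelity to the trial's population. It does not cover an unbled lesion or a coagulation defect that 2a would not catch and no specific covariate describes.

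The header may have been meant for surgery only. The flowchart counts do not reveal which window was run, but the text would still need to say so. Section 5.2.2 calls the criteria adapted, and Appendix A's colour key grades mapping quality, so 2b may already be marked as imperfect. Neither explains why a standing condition has a shorter window here than in 1e. The codes 286.x and 287.x are not confined to chronic disorders, so a short window is defensible for part of that list, most clearly thrombocytopenia.

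A reader might infer that most affected patients stay in. Assuming one code every 60 to 180 days, a 31-day window catches 31/60 = 52% down to 31/180 = 17% and misses 48% to 83%. That coding frequency appears nowhere in the documents, and the proxies in the working fall on both sides of one half. The low end would also imply 1,235/(31/180) ≈ 7,170 Optum patients with an item 2 code, or 14.4% of 49,717.

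**Conclusion.** The point holds as a mismatch between the trial criterion and its implementation. The 30-day window belongs to surgery, and as printed it also governs two conditions for which the trial states no limit. Patients whose only code is older than 30 days can enter the cohort.

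Their number is not reported. The 30% to 68% missed is an illustration that assumes coding follows visit patterns. It neither shows nor rules out that most are missed.

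The documents also do not support inferring a biased hazard ratio. Before matching, the share of cardiologist patients seen in the last 30 days differed by arm (64.8% warfarin, 80.1% rivaroxaban). After matching it was close: 31,664/39,775 = 79.6% versus 31,170/39,876 = 78.2%. Measuring history of intracranial bleeding over 180 days is a separate choice, in line with most exclusions, and does not follow from the surgery window.

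**What to change.** State a window for each 2b item:

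- Item 1 (surgery): keep 30 days.
- Item 3 (intracranial lesions): 180 days.
- Item 2 codes other than 287.3x-287.5x: 180 days.
- Thrombocytopenia (287.3x-287.5x): take it out of item 2 and leave it to 2d's 30 days.
- Report the patients removed by each item in the flowchart.

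Section 5.1 already requires 180 days of enrollment, so no new data are needed.

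An all-available look-back for lesions or bleeding history should be at most a sensitivity analysis. Before matching, prior database time differs by arm in Medicare (mean 953 days for warfarin, 824 for rivaroxaban, standardized difference 0.22), so an open-ended exclusion could be detected unequally.

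The cost is a rerun of the cohort, matching, balance tables and final power, and a somewhat smaller cohort whose size cannot be computed from the documents. Power is unlikely to be an obstacle. The plan's pooled superiority figure reproduces as Φ(√(1,034.57/4) × |ln 0.79| − 1.96) = 0.966. With 5.6% fewer events (976.6, the upper illustration above) it is about 0.96.

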Appendix A

#	ROCKET-AF trial definitions	Implementation in routine care	References/Rationale	Color coding
	Trial details- Primary indication, 4a- Unintended S with label change HR = 0.79 (95% CI 0.66-0.96)		
Please see the following Google Drive for further details or any missing information: https://drive.google.com/open?id=1WDb18wvwIIfakell7cuK-VCmb6b-gV
	Criteria
			
ICD-10 codes are not listed in this document because of excel file size limitations and excessive number of ICD-10 codes. Full ICD-10 code lists will be available in the above Google Drive Folder (link above). ICD-9 to ICD-10 code conversions were completed using a SAS macro that implements forward/ backward mapping based on the CMS ICD-9 to ICD-10 mapping: https://www.ncbi.nlm.nih.gov/pmc/articles/PMC3070730/
	Adequate mapping in claims
		EXPOSURE vs. COMPARISON		
	Rivaroxaban vs. Warfarin	Rivaroxaban 20mg OR 15mg daily (if low GFR) vs. adjusted-dose warfarin		Intermediate mapping in claims
		PRIMARY OUTCOME		Poor mapping or cannot be measured in claims

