	Primary endpoint of stroke (ischemic or hemorrhagic) and systemic embolism.	Measured 1 day after drug initiation in primary diagnosis position specified below and inpatient care setting: Stroke: ICD-9 discharge diagnosis codes: 430.xx Subarachnoid hemorrhage (SAH) 431.xx Intracerebral hemorrhage (ICH) 433.x1 Occlusion and stenosis of precerbral arteries with cerebral infarction 434.xx (excluding 434.x0) Occlusion and stenosis of cerebral arteries with cerebral infarction 436.x Acute, but ill-defined cerebrovascular events Systemic embolism: ICD-9 discharge diagnosis code: 444.xx Arterial embolism ICD-10 discharge diagnosis code: I74.x Arterial embolism and thrombosis	
For stroke: PPV of 85% or higher for ischemic stroke PPV ranging from 80% to 98% for hemorrhagic stroke →[Andrade SE, Harrold LR, Tjia J, et al. A systematic review of validated methods for identifying cerebrovascular accident or transient ischemic attack using administrative data. Pharmacoepidemiology and Drug Safety 2012;21 Suppl 1:100-28.] →[Tirschwell DL, Longstreth WT, Jr. Validating administrative data in stroke research. Stroke; a journal of cerebral circulation 2002;33:2465-70.] →[Roumali CL, Mitchell E, Gideon PS, Varas-Lorenzo C, Castellsague J, Griffin MR. Validation of ICD-9 codes with a high positive predictive value for incident strokes resulting in hospitalization using Medicaid health data. Pharmacoepidemiology and drug safety 2008;17:20-6.]
	Can't be measured in claims but not important for the analysis
		INCLUSION CRITERIA		
1	Men or women aged ≥18 years	Measured on the day of drug initiation: Age >=18		
2	Non-valvular Atrial fibrillation Atrial fibrillation must be documented by ECG evidence (e.g., 12-lead ECG, rhythm strip, Holter, pacemaker interrogation) within 30 days before randomization. In addition, subjects must have medical evidence of atrial fibrillation within 1 year before and at least one day before the qualifying ECG evidence. This could be obtained from a notation in the subject's record (e.g., medical chart, hospital discharge summary).	Measured 12 months prior to and including day of drug initiation, with >2 diagnoses separated by at least 14 days, in any diagnosis position and inpatient or outpatient care setting: Atrial fibrillation: ICD-9 diagnosis: 427.31 ICD-10 diagnosis: I48.0x, I48.1x, I48.2x, I48.9x		

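### The claims definition of intracranial neoplasm (exclusion 2b) lists only benign-tumour codes, so step 2b.3 does not remove malignant or metastatic brain tumours

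*Combined protocol and SAP*

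**What the plan says.** In Appendix A, exclusion 2b, the trial-definition column includes "Known intracranial neoplasm, arteriovenous malformation, or aneurysm", with no restriction to benign tumours. The routine-care column implements the neoplasm part as "ICD-9 diagnosis: 225.xx ICD-10 diagnosis: D33.xx". The window is "Measured 30 days prior to and including day of drug initiation in diagnosis position and inpatient or outpatient care setting". The point made here does not depend on the length of that window.

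The flowchart in section 5.3 reports the step in one row, "Excluded based on Exclusion #2b.3 - Intracranial neoplasm, AV malformation, cerebral aneurysm", so the neoplasm component has no count of its own.

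The note at the head of Appendix A says that the complete ICD-10 lists are kept in an external folder because they are too long to print. It adds that "ICD-9 to ICD-10 code conversions were completed using a SAS macro". The primary-outcome row counts subarachnoid (430.xx) and intracerebral (431.xx) hemorrhage as stroke.

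**The concern.** The trial placed intracranial neoplasm among its hemorrhage-risk exclusions. A replication that follows the printed codes removes the benign part of that group and leaves the malignant part to be caught, if at all, by other rules. The retained patients belong to a group that the trial treated as a bleeding risk. Brain hemorrhage is a component of the primary outcome, and major bleeding is the control outcome in section 6.3.1.

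Section 5.2.2 says that the criteria follow the trial as closely as possible. Where claims cannot capture a criterion, as in 1c and 1d, Appendix A says so. For 2b it gives no reason for the narrower definition, which therefore reads as an oversight in the code list. At stake is fidelity to the trial population and, in principle, a few outcome events from patients whom the trial would not have enrolled.

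**Working it through.** **1. Code content.** Appendix A does not label 225.xx or D33.xx. Their meaning here comes from the public ICD classification: both are the benign families for the brain and nervous system. The plan points the same way one page earlier, where exclusion 1e labels 212.7 and D15.1 as benign neoplasm of the heart. No row of Appendix A prints a code for a malignant primary or secondary brain tumour.

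**2. Could the ICD-10 conversion close the gap?** The conversion runs from ICD-9 to ICD-10. Mapping a benign ICD-9 family does not produce malignant or secondary codes. The gap is in the ICD-9 source list and carries into both coding eras.

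**3. Could other exclusions close it?**
- 4a (life expectancy under 2 years) runs through the comorbidity index with no printed cut-off. It removes 40 + 31 + 400 = 471 patients.
- 3h removes anemia coded as due to neoplastic disease or chemotherapy.
- 2a removes recent bleeding, including intracranial bleeding, within 180 days.

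Each may take out some affected patients. None identifies brain tumours.

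**4. Size of the existing step (section 5.3).** Row 2b.3 removes 259 + 283 + 422 = 964 of 48,482 + 56,256 + 158,888 = 263,626 patients, or 0.37%, for neoplasm, malformation and aneurysm together. The subtraction is correct in all three databases.

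**5. Number affected.** The documents give no prevalence, so 0.1% to 0.3% is an assumption.
- Before matching: 40,604 + 50,085 + 133,230 = 223,919. Times 0.001 is 224, and times 0.003 is 672.
- Matched (section 10): 102,636. Times 0.001 is 103, and times 0.003 is 308.

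**6. Power.** The plan's pooled figures reproduce. Expected events are d = 102,636 × 10.08/1,000 = 1,034.57. Power is Φ(√(d/4)·|ln HR| − 1.96).
- Superiority, HR 0.79: Φ(16.08 × 0.2357 − 1.96) = 0.9665 (plan: 0.96645).
- Non-inferiority, margin 1.46 and true HR 1: Φ(16.08 × 0.3784 − 1.96) = 0.99998 (plan: 0.99998).

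Suppose wider codes removed between 0.05% and 1% of matched patients (assumed; 51 to 1,026 patients). Events would fall to between 1,034.1 and 1,024.2, and superiority power to between 0.9664 and 0.9650. Non-inferiority power would stay above 0.9999.

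**7. Hazard ratio.** Assume a prevalence f of 0.05% to 0.5% among matched patients and an event rate k = 3 to 10 times that of other patients. The share of events from these patients is fk/(1 − f + fk).
- f = 0.0005, k = 3: 0.0015, or 1.6 events.
- f = 0.005, k = 10: 0.0478, or 49.5 of 1,035 events.

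Now suppose they are split 2:1 between arms, so that f₁ = 4f/3 and f₀ = 2f/3. The hazard ratio shifts by about (1 + f₁(k − 1))/(1 + f₀(k − 1)).
- f = 0.0005, k = 3: 1.00133/1.00067 = 1.001.
- f = 0.005, k = 10: 1.06/1.03 = 1.03.

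**The case against.** The strongest reply has four parts.

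- **The code meanings are external.** Appendix A never says that 225.xx and D33.xx are benign, so this is not an internal contradiction. That is true. The point rests on a public classification, which is enough to read a code list.
- **Mapping quality may already be flagged.** Appendix A grades each row by colour, and the colours are not legible in the text. The row may already be marked as imperfect. That would acknowledge the limit but would not explain why the malignant codes were left out.
- **Other exclusions overlap.** A reader might infer that every patient with a malignant brain tumour stays in the cohort. The documents do not support that, because 4a, 3h and 2a can each remove some. What stands is that 2b.3 does not remove them.
- **The printed ICD-10 cell is not the implemented list.** A reader might infer that meningioma is dropped in ICD-10 and that the rule changes at the coding switch, because D32.x is not printed while 225.xx includes the cerebral meninges (225.2). This is not shown. The full ICD-10 lists are held elsewhere and were mapped from ICD-9, so the implemented list may well contain the meninges code. It needs checking.

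A reader might also infer a biased comparison. Nothing in the documents shows that anticoagulant choice differs in these patients. In Appendix B, prior cancer is balanced after matching: 6,326 (12.3%) on warfarin against 6,242 (12.2%) on rivaroxaban, standardized difference 0.00. Balance on any cancer does not prove balance on brain tumours, but there is no evidence of imbalance.

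**Conclusion.** The point holds as a small fidelity correction. As printed, step 2b.3 is narrower than the trial criterion that it emulates, and it leaves malignant primary and metastatic brain tumours to incidental removal by other rules in both coding eras. This rests on the standard meaning of the two code families.

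The number affected cannot be derived from the documents, and the counts in the working are only as good as the assumed prevalence. Over the assumed ranges, the hazard ratio shifts by a factor of 1.001 to 1.03, and that requires a 2:1 imbalance that nobody has shown. Power barely moves. The conclusion of the study is not threatened; the correction has low priority but is easy to make.

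**What to change.** - Add 191.x and 198.3 to the ICD-9 list, and C71.x and C79.31 to the ICD-10 list, or state why they are omitted.
- Check that the implemented ICD-10 list contains the cerebral meninges code in D32.x. Add it if it does not.
- Restrict all lists to intracranial sites, dropping spinal-only codes.
- Print the implemented ICD-10 list for 2b in Appendix A.
- Re-run 2b.3, matching and balance, and report the count removed by the neoplasm component alone.

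The cost is a code-list edit and a re-run, with probably at most a few hundred fewer patients. Section 13 carries no date for the comparative analyses, so the document records no comparative result that the change would disturb.
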